7.6. Assessments

7.6.1. Physical Examination

At the Baseline Visit (Visit 1) height and weight will be documented.

7.6.2. Prognostic Factors

Prognostic factors will be determined at the Baseline Visit (Visit 1) based on prior medical history. The EULAR recommendation for the management of rheumatoid arthritis with synthetic and biological disease-modifying antirheumatic drugs [12] defines the following poor prognostic factors:

- Moderate (after conventional synthetic DMARD [csDMARD] therapy) to high disease activity according to composite measures
- High acute phase reactant levels
- High swollen joint counts
- Presence of RF especially at high levels
- Presence of ACPA, especially at high levels
- Combinations of the above
- Presence of early erosions
- Failure of two or more csDMARDs

7.6.3. Insurance Type

Insurance type will be documented at the first visit (baseline visit). Patients can either have statutory health insurance or private insurance.

7.6.4. Varicella vaccination status

At the Baseline Visit (Visit 1) current varicella vaccination status of patients will be assessed.

7.6.5. Treatment of Rheumatoid Arthritis (RA-Treatment) with Tofacitinib and/or other DMARDs

At each visit (visits 1-9) dose and route of administration (if applicable) of treatment with Tofacitinib and/or other DMARDs will be documented. If an escalation (as defined in section 6.1.1) occurred since the last visit, in addition stop date of previous DMARD(s), start date of new DMARD(s) and reason for switch (lack of efficacy or intolerance) will be documented.

7.6.6. Concomitant treatment for rheumatoid arthritis with glucocorticoids

At each visit (visits 1-9) dose and route of administration of concomitant treatment with glucocorticoids will be documented.

7.6.7. Effectiveness criteria

The effectiveness of the treatment with Tofacitinib will be documented using the following tools for the evaluation of the course of the disease:

Table 8. Disease Activity Indicators

Indicator	Definition/Calculation
DAS28-4 (CRP)	$0.56*\sqrt{(TJC28)} + 0.28*\sqrt{(SJC28)} + 0.36*\ln(CRP \text{ in mg/l} + 1) + 0.014*PtGA \text{ in mm} + 0.96$
DAS28-4 (ESR)	$0.56*\sqrt{(TJC28)} + 0.28*\sqrt{(SJC28)} + 0.70*\ln(ESR \text{ in mm/hour}) + 0.014*PtGA \text{ in mm}$
Simplified Disease Activity Index (SDAI)	$(TJC28) + (SJC28) + [\text{PhyGA in cm}] + [\text{PtGA in cm}] + [\text{CRP in mg/dL}]$
Clinical Disease Activity Index (CDAI)	$(TJC28) + (SJC28) + [\text{PhyGA in cm}] + [\text{PtGA in cm}]$
ACR/EULAR Boolean-based definition of remission	A patient must satisfy all of the following: tender joint count ≤ 1 , swollen joint count ≤ 1 , CRP $\leq 1 \text{ mg/dL}$, subject's global assessment of arthritis ≤ 1 on a 0-10 scale

TJC = tender joint count; SJC = swollen joint count; CRP = C-reactive protein in mg/L; ESR = erythrocyte sedimentation rate in mm/first hour, PtGA = Patient's Global Assessment of Arthritis; PhyGA = Physician's Global Assessment of Arthritis

7.6.8. Joint Counts

7.6.8.1. Tender/Painful Joint Count (TJC28)

Twenty-eight (28) joints will be assessed to determine the number of joints that are considered tender or painful. The 28 joints to be assessed are the shoulders, elbows, wrists, metacarpophalangeal (MCP) joints, proximal interphalangeal (PIP) joints, and knees. Artificial joints will not be assessed.

The response to pressure/motion on each joint will be assessed.

7.6.8.2. Swollen Joint Count (SJC28)

The 28 swollen joint count includes the following joints: shoulders, elbows, wrists, metacarpophalangeal joints (MCP), proximal interphalangeal joints (PIP), and knees. Artificial joints will not be assessed.

The swelling of each joint will be assessed.

7.6.9. Patient Assessment of Arthritis Pain

Patients will assess the severity of their arthritis pain using a 100 mm visual analog scale (VAS) by placing a mark on the scale between 0 (no pain) and 100 (most severe pain), which corresponds to the magnitude of their pain. "How severe is your pain today? Place a vertical mark on the line below to indicate how bad you feel your pain is today."

7.6.10. Patient Global Assessment of Arthritis (PtGA)

Patients will answer the following question, “Considering all the ways your arthritis affects you, how are you feeling today?” The patient’s response will be recorded using a 100 mm VAS with anchors on 0 = very well and 100 = very poorly.

7.6.11. Physician Global Assessment of Arthritis (PhyGA)

The HCP will assess how the patient’s overall arthritis appears at the time of the visit. This is an evaluation based on the patient’s disease signs, functional capacity and physical examination, and should be independent of the Patient’s Global Assessment of Arthritis. The HCP’s response will be recorded using a 100 mm VAS with 0 mm = no disease activity and 100 mm = worst disease activity. “Physician’s Global Assessment of Rheumatoid Arthritis. Place a vertical mark on the line below to indicate the Disease Activity.”

7.6.12. Duration of Morning Stiffness

The duration of morning stiffness will be determined by asking the following questions: “When you wake up in the morning, do you currently suffer from morning stiffness?” “How long does the morning stiffness last from the time you wake up?”

7.6.13. Functional Ability Questionnaire Hannover (FFbH)

The FFbH for RA is a German Short questionnaire for the assessment of patientive functional capacity in the context of basic everyday activities (range: 0-100% functional capacity)[18]. Functional remission in FFbH is defined as functional capacity > 83 %.

7.6.14. EuroQoL EQ-5D-3L Health State Profile

The EuroQoL EQ-5D-3L Health State Profile[19] is a copyrighted, patient completed instrument designed to assess impact on health-related quality of life in five domains: mobility, self-care, usual activities, pain/discomfort, and anxiety/depression. Additionally, scores from the five domains may be used to calculate a single index value, also known as a utility score. The validity and reliability of the EuroQoL EQ-5D-3L has been established in a number of disease states, including rheumatoid arthritis. The form should then be checked by site staff for completeness.

7.6.15. Functional Assessment of Chronic Illness Therapy (FACIT) - Fatigue Scale

The FACIT – Fatigue Scale is a patient completed questionnaire[20]consisting of 13 items that assess fatigue. Instrument scoring yields a range from 0 to 52, with higher scores representing better patient status (less fatigue). This questionnaire should be completed by the patient prior to any procedures being performed at the visit, if possible. The form should then be checked by site staff for completeness.

7.6.16. Patient’s satisfaction with drug treatment

Satisfaction with treatment will be assessed on a 5-point Likert scale (where 0 = extremely dissatisfied, 1= dissatisfied, 2 = neither satisfied nor dissatisfied, 3 = satisfied

and 4 = extremely satisfied) in response to the question “How satisfied are you with the drugs that you have received for your arthritis since your last visit?”

7.6.17. C-reactive Protein (CRP)

The CRP shall be analysed by a local laboratory according to usual practice. It will be used in the calculation of several efficacy parameters.

7.6.18. Erythrocyte Sedimentation Rate (ESR)

The ESR shall be analysed by a local laboratory according to usual practice. It will be used in the calculation of several efficacy parameters.

7.6.19. Safety

All adverse events (AEs) that will occur during the observation period will be documented. At the final visit or if a patient is switched from Tofacitinib to another DMARD, the HCP will be asked to assess the general tolerability of the treatment with Tofacitinib and the reasons for discontinuation (intolerability or lack of efficacy) will be analysed.. Patient's satisfaction with drug treatment will be assessed as described in section 7.6.16.

7.7. Study size

The analysis of the primary endpoint is a time to event analysis, where the event is treatment escalation. It is possible for multiple events to occur for each patient within the follow-up period. The primary analysis aims to investigate which of the factors listed actually affect the rate at which a patient's treatment is changed. In order to determine an appropriate sample size for this study recurrent event data was simulated, using the methods described by Jahn-Eimermacher *et al.* (2015), and analysed using cox proportional-hazards models.[21]

The distribution of each of the factors was obtained from the ORAL STANDARD study:

Achieve DAS28 < 3.2	-	Binomial(n, 0.2)
Achieve Δ DAS28 > 1.8	-	Binomial(n, 0.6)
Δ Patient Global Assessment	-	Normal(-29.31, 38.579 ²)
Δ Physician Global Assessment	-	Normal(-27.01, 30.966 ²)
Δ Pain score	-	Normal(-34.99, 24.672 ²)

The baseline hazard rate was assumed to be 3.16 events per patient over the follow-up period.

The impact of each the factors on the hazard rate, (entered as the regression coefficient), is used to simulate the event times for each patient given their values for the simulated factors. The regression coefficients were assumed to be (-0.288, -2.303, -0.01, -0.01, -0.01). Simulations were carried out for sample sizes ranging from 100 to 4,500.

Figure 2 shows the power to detect an effect of each factor against sample size for the 5 different factors.

[figure not shown]

Figure 2: Plot of Power against Sample Size for simulations of recurrent event data analysed using cox-proportional hazards model including all 5 factors of interest.

Given the initial assumptions the power to detect an impact of 4 of the 5 factors, within the full cox proportional hazards model was greater than 80% with a sample size of 1000 patients. The power to detect an effect of the remaining factor, achieving $DAS28 \leq 3.2$, was around 50% for 1500 patients and 60% for 2000 patients. The power is very high for $\Delta DAS28 > 1.8$, mainly due to the high proportion of patients assumed to achieve the criteria and the high impact achieving the criteria is assumed to have on the rate of treatment escalation (significantly reducing it).

Sensitivity analyses were carried out around the assumptions made for the simulations. Full details of the sensitivity analyses will be included in the SAP.

Based on the results of the initial simulation and of sensitivity analyses, it is deemed that 1500 patients should provide a reasonable sample size on which to draw conclusions of the effect of the achieving change from baseline in $DAS28 > 1.8$ and the patient/physician VAS scores on the rate of treatment escalation. Based on sensitivity analysis, if achieving $DAS28 \leq 3.2$ does in fact have a bigger effect on the event rate than initially assumed there should be sufficient power to detect this effect.

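### Protocol 7.7: the printed simulation inputs do not give the stated LDA power, the VAS coefficients run against the DAS28 terms, and the promised sensitivity analyses are not in the SAP body

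*Protocol*

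**What the plan says.** Protocol 7.7 simulates recurrent escalations and fits a Cox model with five factors.

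- **Baseline:** "The baseline hazard rate was assumed to be 3.16 events per patient over the follow-up period".
- **Factors:** LDA with probability 0.2; DAS28 change > 1.8 with probability 0.6; changes in patient global, physician global and pain, normal with means −29.31, −27.01 and −34.99 and SDs 38.579, 30.966 and 24.672.
- **Effects:** "The regression coefficients were assumed to be (-0.288, -2.303, -0.01, -0.01, -0.01", in that order.
- **Power:** four factors exceed 80% at 1000 patients. For the fifth, LDA, power "was around 50% for 1500 patients and 60% for 2000 patients". The very high power for DAS28 change is put down partly to "the high impact achieving the criteria is assumed to have on the rate of treatment escalation (significantly reducing it".
- **Sensitivity analyses:** "Full details of the sensitivity analyses will be included in the SAP". The section closes by saying that if LDA "does in fact have a bigger effect on the event rate than initially assumed there should be sufficient power to detect this effect", and it attributes this to those analyses. It ties the choice of 1500 to DAS28 change and the VAS scores.

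The scale directions are in Protocol 7.6.9 to 7.6.11. Pain is rated by "placing a mark on the scale between 0 (no pain) and 100 (most severe pain", and patient global uses a "100 mm VAS with anchors on 0 = very well and 100 = very poorly". The physician scale runs the same way.

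For the simulation, 7.7 states no significance level, correlation between factors, frailty, hazard shape or censoring.

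**The concern.** An LDA hazard ratio of exp(−0.288) = 0.75 in a fifth of 1500 patients, with a baseline of 3.16 events each, should be easy to detect. Power of about 50% therefore looks out of line with its own inputs. The VAS terms also point the wrong way: a negative coefficient on a change that is negative when patients improve makes improvement a driver of escalation.

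LDA is the treat-to-target benchmark that motivates the study (Protocol 5) and the first factor listed for the primary model (Protocol 7.9.2.1). If it shows no effect in the final model, a reader must know whether the study had about an even chance of detecting the assumed effect or was almost certain to. The documents do not settle this, and the one reassurance they offer rests on analyses that they do not show.

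**Working it through.** **1. Events needed for the stated power.** Schoenfeld's formula, with p = 0.2, β = −0.288 and two-sided 0.05 (assumed), is d = (1.96 + z_power)² / [p(1 − p)β²]. The denominator is 0.16 × 0.0829 = 0.01327.

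- 50% power: 1.96² / 0.01327 ≈ 290 events, or 290/1500 = 0.19 per patient.
- 60% power: (1.96 + 0.253)² / 0.01327 ≈ 370 events, or 370/2000 = 0.185 per patient.

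A stricter alpha does not explain the gap. By the same formula, 1500 events still give 88% power at two-sided 0.001.

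**2. Events the inputs imply (independent factors).**

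- DAS28 terms: (0.8 + 0.2 × 0.75) × (0.4 + 0.6 × 0.10) = 0.95 × 0.46 = 0.437.
- VAS terms at the means: exp(0.01 × (29.31 + 27.01 + 34.99)) = exp(0.9131) = 2.49 as printed; 0.40 with signs reversed.
- VAS variance term: 0.5 × 0.0001 × (38.579² + 30.966² + 24.672²) = 0.153.
- Events per patient as printed: 3.16 × 0.437 × exp(0.913 + 0.153) ≈ 4.0.
- Events per patient with VAS signs reversed: 3.16 × 0.437 × exp(−0.913 + 0.153) ≈ 0.65.

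As printed, that is about 6,000 events at 1500 patients. The sign alone changes the count about six-fold (4.0/0.65).

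**3. Direction.** On scales where 100 is worst, a negative change is improvement. A coefficient of −0.01 then multiplies the hazard by 2.49 at the mean improvement, while the DAS28 terms multiply it by 0.75 and 0.10.

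**4. Simulated LDA power.** Assumptions: constant baseline 3.16, time-fixed factors, full follow-up, two-sided 0.05. Under these the Andersen-Gill model is equivalent to Poisson regression on counts. Robust standard errors are used wherever there is gamma frailty. Monte Carlo error is about 1 point at 2000 runs per cell; ranges show repeat simulations.

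| Setting | 1500 | 2000 |
|---|---|---|
| Stated in Protocol 7.7 | about 50% | 60% |
| Printed signs, independent | 100% | 100% |
| Printed signs, LDA nested in DAS28 change | 95% | 99% |
| Printed signs, first event only | 96% | 99% |
| Printed signs, frailty variance 2 | 52% | 65% |
| Reversed signs, independent | 92% | 97% |
| Reversed signs, correlation 0.5 among all factors | 51–55% | 64–67% |
| Reversed signs, correlation 0.4 plus frailty variance 0.5 | 47–50% | 57–62% |
| Reversed signs, 92% of LDA patients also meet DAS28 change | 52% | 66% |
| Reversed signs, frailty variance 1.5 | 48% | 61% |

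The Prentice-Williams-Peterson gap-time model, the alternative in SAP 9.1.1, gives 100%/100% with printed signs and about 92%/98% with reversed signs (independent factors). The settings that come near 50%/60% are examples; the list is not exhaustive.

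**5. The other four factors.** In the settings above that come near the stated LDA power, the weakest of the other four has about 91% power or more at 1000. That agrees with the protocol's statement of more than 80%.

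**6. The SAP.** SAP 3.1 repeats the target of about 1500. The sensitivity analyses in SAP 7.3.2, 9.2.2 and 9.2.6 vary the covariates, the analysis set and the visit to which a switch is assigned. None varies a simulation assumption, and no section of the SAP body deals with study size.

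**The case against.** The strongest reply is that this is under-reporting rather than a wrong figure. Protocol 7.7 prints marginal distributions only. It never says that the factors were independent, that frailty was absent or that follow-up was complete; I supplied those settings. The event-generating method is in a cited paper and the power curves are in Figure 2, neither of which can be seen here. Modest settings come close to the stated figures: reversed VAS signs with correlation 0.5, or 0.4 with a small frailty, keep the other four factors at 98% or more at 1000. The section also counts improvement as positive for DAS28 change but as negative for the VAS changes, so the VAS sign could be a slip of notation. The sign conflict and the power mismatch may then share one cause. This all stands, and it rules out saying that the stated power is wrong.

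It is also true that little turns on this operationally. SAP section 5 is descriptive apart from the primary model. Three interim analyses are already done (SAP 4.1), and no re-run can change the design now.

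What does not yield is what is on the page. The section presents its power as following from the initial assumptions that it prints, and they do not give it. The VAS direction contradicts the scale definitions whatever the code did. The sensitivity analyses were promised and then relied on.

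A reader might go further and infer that 1500 is too few, or that LDA is in truth amply powered. The documents support neither. Protocol 7.7 rests 1500 on DAS28 change and the VAS scores, and near-100% LDA power depends on independence and no frailty. Protocol 7.12 itself warns that the factors may be highly correlated.

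**Conclusion.** The point holds as an inconsistency between printed inputs and stated power, together with a sign conflict and an undelivered commitment. Taken at face value the inputs overshoot the stated LDA power by about 50 points at 1500 and 40 at 2000. After reversing the VAS signs the gap is still about 42 and 37 points. Closing it takes assumptions that are not printed. These sizes rest on independent factors, no frailty, constant hazard, full follow-up and two-sided 0.05.

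Whether the notation, the code or the reporting is at fault cannot be told from the documents. The consequence is for interpretation: a null LDA result could not be read against a known power, and the closing reassurance about a larger LDA effect cannot be checked.

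**What to change.** 1. Reconcile the VAS coefficients in Protocol 7.7 with the scale directions in 7.6.9 to 7.6.11, and say whether the text or the code was at fault.
2. Re-run the simulation with factor correlation, frailty, censoring and alpha stated. Put the VAS terms on the scale the model uses: SAP 7.3.1 enters the 0–100 mm value, whereas 7.7 simulates change.
3. Restate power for each factor at 1500 in Protocol 7.7.
4. Either put the simulation sensitivity analyses in the SAP, or withdraw the statement that a bigger LDA effect would have sufficient power.

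The cost is one re-run of existing code, a corrected paragraph and a short SAP section. The restated LDA power may go up or down. No change in enrolment is needed.

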7.8. Data management

Patients' personal data will be collected, stored and processed exclusively in pseudonymised form in accordance with the national data protection laws. All data will remain in pseudonymised form. The data will not be used for any other purposes other than for the research which is described in the patient information and the declaration of consent. Pfizer undertakes responsibility to guarantee data protection and will adhere to all applicable laws and regulations on data protection.

All study data will be recorded by the study sites in the electronic data capture (EDC) system Clincase (Quadrattek Data Solutions Ltd.). Clincase fulfills all requirements of 21 Code of Federal Regulations (CFR) Part 11 and the central server situated in Germany is backed up once a day. Access to the system takes place via a secure website (Secure Sockets Layer (SSL) encryption). Access is only given to registered users who log in with a unique user name and password. Depending on their function in the study, individual users are assigned defined access rights. Access rights to the EDC system are monitored by authorised Advanced Medical Services GmbH (AMS) employees.

Documentation by physicians will take place using paper questionnaires or eCRF masks. Patient questionnaires will be handed out in paper form and entered in the EDC system by AMS. Automatic checking of the data for plausibility and completeness using programmed so-called edit checks will take place already during electronic data entry by the study site. Other discrepancies will be clarified additionally with the study site using manual queries.

Due to the non-interventional nature of the study, the extent of data cleansing is limited and missing and/or implausible values are to be anticipated at the end of the study. In the statistical analysis plan, handling of these values will be described in detail.

Confirmation of the data collected is required by the physician's electronic signature.

Please refer also to previous sections [7.2](#), [7.3](#) Variables, and [0](#) Data sources

7.9. Data analysis

This section gives an overview of the key methods and derivations required for the study. Detailed methodology for summary and statistical analyses of data collected in this study will be documented in a Statistical Analysis Plan (SAP), which will be dated, filed and maintained by the sponsor. The SAP may modify the plans outlined in the protocol; any major modifications of primary endpoint definitions or their analyses would be reflected in a protocol amendment. SAS (Version 9.1, 9.2, 9.3 or 9.4) will be used for all analyses.

7.9.1. Analysis Populations

The Full Analysis Set is defined as patients who receive at least one dose of Tofacitinib and have at least one set of post-baseline measurements. This population will be used for all efficacy analysis. Details of any methods employed to deal with missing data will be outlined in the SAP.

The Safety Analysis Set is defined as all patients who receive at least one dose of Tofacitinib. This population will be used for all safety analysis.

7.9.2. Efficacy Analysis

7.9.2.1. Primary analysis

The primary analysis will investigate the impact of various factors on the rate of treatment escalation. Cox proportional-hazards modelling will be used, with status of each patient (whether they experienced a treatment escalation or not) and the times of such treatment escalations being used for the baseline model.

The factors that will be investigated and thus included in the model will be:

- whether or not a patient achieves LDA, as defined by DAS28-4 (ESR) ≤ 3.2 .
- whether or not a patient achieves change from baseline in DAS28-4 (ESR) > 1.8
- Patient's Global Assessment of Arthritis
- Physician Global Assessment of Arthritis
- Patient's Assessment of Arthritis Pain
- Patient's satisfaction with drug treatment

If patients withdraw or are lost to follow-up they will be censored at the time of the last available visit.

7.9.2.2. Secondary Analysis

7.9.2.2.1. Time to Event Analysis

Time to event endpoints will be investigated using Kaplan-Meier methodology and, where appropriate, Cox-Proportional Hazards modelling will be used to look at differences in event rate between sub-groups. The time to event will be summarised in terms of medians and confidence intervals. Kaplan-Meier plots of the time to event over the study duration will be presented.

